### 7.1.3 Safety Population

The Safety analysis population will include all patients in the ITT population who receive at least one dose of study drug. Subjects within the Safety population will be summarised under the treatment they actually received. The treatment received will be identified by merging the randomisation schedule with the study drug administration page of the Case Report Form (CRF) by the IMP box number, if available. Any patients who receive SNG001 at any time will be summarised under the SNG001 treatment arm. Patients who receive placebo for every dose will be summarised under the placebo treatment arm. The safety population will be used for analysis and summaries of safety endpoints.

CCI

CCI

### 7.1.5 Immunogenicity Population

The Immunogenicity Population will include patients enrolled at sites where immunogenicity sample collection was feasible and who have at least one valid immunogenicity result.

## 7.2 Covariates and Subgroups

The variables below have been selected because they are probable risk factors relating to severity and recovery from SARS-CoV-2.

The following subgroups will be analysed:

- Age category:
  - < Median age
  - $\geq$  Median age
  - <40
  - 40 - 49
  - 50 - 65
  - 66 - 75
  - >75
- Co-morbid conditions at screening of cancer, cerebrovascular disease, chronic kidney disease, chronic lung diseases, chronic liver disease, diabetes mellitus type 1 and type 2, heart conditions (such as heart failure, coronary artery disease, or cardiomyopathies), mental health disorders or tuberculosis. These comorbidities are listed by the Centres for Disease Control and Prevention [11] as supported by at least one meta-analysis or systematic review. Obesity and smoking are also listed as comorbidities, however these are covered by other subgroups listed below.
  - Does not have comorbidity at screening.
  - Has one comorbidity at screening

## Statistical Analysis Plan (RotW)

Final v1.0, 08FEB2022

SG018

- Has more than one comorbidity at screening
- Current smoking status:
  - Current smoker
  - Current e-cig user
  - Former smoker
  - Does not smoke
- Sex:
  - Male
  - Female
- BMI category:
  - < 30
  - $\geq 30$
- Race:
  - White
  - Non-White
- Prior duration of symptoms (in days):
  - < Median duration
  - $\geq$  Median duration
  - $\leq 7$
  - $> 7$
- Geographic region (See [Section 7.5](#))
- Breathlessness at Baseline
  - 4
  - < 4
  - $\geq 3$
  - < 3
  - $\geq 2$
  - < 2
- COVID-19 vaccine status at randomisation:
  - No prior COVID-19 vaccination
  - Partially vaccinated
  - Fully vaccinated (two doses received for vaccines required to be double dosed, or one dose received for vaccines required to be a single dose [e.g. Janssen/Johnson and Johnson vaccine]).
- S/F Ratio at randomisation will be categorised as 'Low', 'Medium' or 'High'. There is no agreed definition for these classifications, therefore the categorisation will be data driven and defined using percentiles:
  - Low ( $\leq 33^{\text{rd}}$  percentile)
  - Medium ( $> 33^{\text{rd}}$  percentile to  $\leq 66^{\text{th}}$  percentile)

## Statistical Analysis Plan (RotW)

Final v1.0, 08FEB2022

SG018

- High (> 66th percentile)

The following variables are factors of interest which have been selected so show homogeneity of the treatment effect:

- COVID-19 Related Therapy at randomisation
  - Remdesivir by any route
  - Corticosteroids by any systemic route (Dexamethasone, Methylprednisolone, Prednisolone, Hydrocortisone)
  - Dexamethasone by any route
  - Dexamethasone administered orally
  - Dexamethasone administered intravenously
- All cases of the above medication use will be included, regardless of whether indicated for COVID-19 or a comorbidity.
- SNG001 Manufacturing Batch
  - SNG001 manufactured using [REDACTED] derived material
  - SNG001 manufactured using [REDACTED] derived material.

The following covariates will be included in statistical models:

- Age as a continuous variable
- Sex:
  - Male
  - Female
- Prior duration of symptoms as a continuous variable
- Geographic region (See [Section 7.5](#))
- COVID-19 vaccine status at randomisation:
  - No prior COVID-19 vaccination
  - Partially vaccinated
  - Fully vaccinated

Patients who receive different types of COVID-19 vaccination will be pooled into a single subgroup.

Only subgroups with at least 20 patients in total will be included in any summaries or analyses.

For analyses of change from baseline for variables other than OSCI the baseline value will also be included as a covariate.

For subgroup analyses the subgroup variable will not be included in the models. The study has not been powered for any of the subgroups defined above, therefore all subgroup analyses should be considered exploratory.

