3.1 Criteria for Inclusion and Exclusion

3.1.1 Inclusion Criteria

To be eligible for randomisation into this study, each patient must fulfil the following criteria:

1. Male or female, ≥ 18 years of age at the time of consent.
2. Admitted to hospital due to the severity of their COVID-19¹.
3. Positive virus test for SARS-CoV-2 using a validated molecular assay or validated antigen assay.

Patients who have a positive virus test for SARS-CoV-2 prior to hospitalisation will be randomised no later than 48 hours after hospital admission. If the virus test is performed more than 96 hours prior to hospitalisation, the test will have to be repeated in the hospital prior to randomisation. Only patients whose repeated virus test is positive will be randomised, no later than 48 hours after confirmation of SARS-CoV-2 infection.

¹ Patients admitted to the hospital for reasons that are non-COVID-19 related, who subsequently develop clinical symptoms of COVID-19, test positive for SARS-CoV-2, and require prolongation of their hospital admission, as a consequence of COVID-19, and require treatment with supplemental oxygen (via nasal prongs or mask), must be discussed with the Sponsor's medical monitor prior to randomisation, to assess suitability for the trial.

Patients who have their first positive virus test for SARS-CoV-2 after hospitalisation will be randomised, no later than 48 hours after confirmation of SARS-CoV-2 infection.

4. Require oxygen therapy via nasal prongs or mask (WHO OSCI score of 4).
5. Provided informed consent.
6. Female patients must be ≥ 1 year post-menopausal, surgically sterile, or using a highly effective method of contraception. Acceptable highly effective methods of contraception include:
 - bilateral tubal occlusion
 - intrauterine device (provided coils are copper-banded)
 - levonorgestrel intrauterine system (e.g., CCI [REDACTED])
 - medroxyprogesterone injections (e.g., CCI [REDACTED])
 - etonogestrel implants (e.g., CCI [REDACTED], CCI [REDACTED])
 - normal and low dose combined oral pills
 - norelgestromin/ ethinylestradiol transdermal system
 - intravaginal device (e.g., ethinylestradiol and etonogestrel), desogestrel (e.g., CCI [REDACTED])
 - total sexual abstinence (defined as refraining from heterosexual intercourse)
 - vasectomised sexual partner.

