### 5.3.1.3 *Progression to Severe Disease or Death within 35 days of First Dose or Randomisation*

Severe disease is defined by the OSCi as a score between 5 and 7. Death is defined by an OSCi score of 8. Any patient with an OSCi score at any post baseline assessment up to and including Day 35 of 5 or more will be considered as progressed to severe disease or death.

All patients should have an OSCi score of 4 at baseline, however in the event a patient is randomised with an OSCi score of  $\geq 5$  at baseline this patient will be excluded from all analyses of progression to severe disease or death.

Day 35 will be determined by the study schedule, which may be more than 35 days after randomisation if randomisation occurs before Day 1.

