### 5.3.9 Derivation of Oxygen Variables

The fraction of inhaled oxygen ( $\text{FiO}_2$ ) can be calculated from the given oxygen flow in L/min using Table 4 below for all devices except the Venturi masks [12].

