**Table 4: Calculation of  $\text{FiO}_2$  for all Devices except Venturi Masks**

Flow (L/min)	$\text{FiO}_2$
1	0.28
2	0.38
3	0.43
4	0.50
5	0.56
6	0.62
7	0.64
8	0.66
9	0.71
10	0.73
11	0.75
12	0.76
13	0.77
14	0.79
15	0.81

Oxygen flow should be taken from the Vital Signs page of the CRF. Any oxygen flow records which are expressed as decimals should be rounded up to the nearest integer. For any oxygen flow records expressed as a range the maximum value should be taken to calculate  $\text{FiO}_2$ .

For Venturi masks the oxygen flow should be presented in the raw data as  $\text{FiO}_2$ . However if the oxygen flow is presented in L/min the standard Venturi mask conversion should be used as per Table 5.

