## 8.3 Demographic and Baseline Variables

The following demographic and baseline information will be summarised for the ITT population. Data collected at the Day 0/ Day 1 visit will be used, unless otherwise indicated below.

- Age
- Sex
- Race
- Ethnic origin
- Care home residence (yes, no)
- Height, weight and BMI at screening.
- Presence of selected co-morbidities (hypertension, cardiovascular disease (excluding hypertension), diabetes, a chronic lung condition or cancer).
- Number of distinct co-morbidities (0, 1, 2, 3+).
- Smoking status (never smoked, former smoker, current tobacco user, current e-cig user).
- Duration of symptoms at baseline.

The summary of demographic and baseline information will be repeated for each of the subgroups defined in [Section 7.2](#). The number and percentage of patients within each subgroup will also be summarised.

A summary of oxygen use at randomisation will also be presented. Summary statistics will be presented for the baseline percentage FiO2, the baseline percentage oxygen saturation and the baseline S/F ratio.

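### The primary Cox models adjust for no measure of severity at entry, although baseline S/F ratio is already derived: the stated power is met, but a cheap, modest gain in power is left unused.

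*SAP*

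**What the plan says.** SAP 7.2 gives one covariate list for all models. Under "The following covariates will be included in statistical models" it names age, sex, prior duration of symptoms, geographic region and COVID-19 vaccine status. SAP 9.1.1.2 applies the list to time to discharge, 9.1.2.2 carries the same method to time to recovery, and 9.2.1.2 applies it to the key secondary logistic models. SAP 7.2 also adds a baseline value as a covariate, but only in change-from-baseline analyses of variables other than OSCI. Protocol 8.5.1 lists treatment arm, age, sex and country/region, and allows the SAP to define more.

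Baseline OSCI carries no information on severity, because "All patients should have an OSCi score of 4 at baseline" (SAP 5.3.1.3), in line with inclusion criterion 4. Randomisation is stratified by site only (Protocol 8.2, SAP 5.2).

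Oxygen need at entry is nevertheless captured. SAP 5.3.9 derives FiO2 and the S/F ratio. SAP 8.3 summarises "the baseline percentage oxygen saturation and the baseline S/F ratio". SAP 7.2 opens its subgroup list with "The variables below have been selected because they are probable risk factors relating to severity and recovery from SARS-CoV-2", and that list contains the item "S/F Ratio at randomisation will be categorised as" low, medium or high. S/F appears in no model as a covariate.

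**The concern.** Every patient enters on low-flow oxygen, but OSCI 4 does not separate a patient on 1 L/min from one on 15 L/min. Neither the design nor the analysis takes account of that difference.

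Two things are at stake. First, leaving a prognostic variable out of a Cox model pulls the treatment hazard ratio toward 1, which costs power. Second, a chance difference between arms in oxygen need goes straight into the estimate. Winning on both primary endpoints matters beyond the headline result, because SAP 7.6 makes it the gate to all three key secondary tests.

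S/F is singled out because, of the listed variables, it is the one that measures oxygen need, the criterion that brings patients into the trial. The SAP's risk-factor statement covers other variables that were also left out of the models, and it does not rank S/F above them.

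**Working it through.** **Inputs from the documents** (Protocol 8.1, SAP 6): 305 per arm; discharge HR 1.45 and recovery HR 1.7; placebo 70% discharged and 30% recovered at Day 28; 25% exponential dropout; two-sided 0.05 with Hochberg; futility stop if both Z < 1.4 in the first 300 patients.

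**The plan's own figure.** With event rate λ and dropout rate μ, the probability of an observed event by Day 28 is λ/(λ+μ) × [1 − exp(−28(λ+μ))], where 28μ = ln(100/75) = 0.288.

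- Discharge: 28λ = ln(100/30) = 1.204 on placebo and 1.45 × 1.204 = 1.746 on SNG001. Probabilities are 0.626 and 0.746; 305 × 1.372 = 418 events. Power = Φ(√418.4/2 × ln 1.45 − 1.96) = Φ(1.84) = 96.7%.
- Recovery: 28λ = ln(100/70) = 0.357 and 1.7 × 0.357 = 0.606. Probabilities are 0.263 and 0.401; 202 events. Power = Φ(√202.4/2 × ln 1.7 − 1.96) = Φ(1.81) = 96.5%.
- Simulated with Hochberg and the futility rule, no covariates: both endpoints 92.2%, at least one 98.5% (independent endpoints); 91.7% and 96.6% with correlation 0.5.

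So the stated 90% and 95% are met at 1.45 and 1.7. The SAP 6 simulation text prints 1.35 for recovery and 1.7 for discharge. On those values power for both endpoints is about 52%. That conflict is a separate matter, and those values are not used below.

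**Assumptions.** The documents give no prognostic strength for S/F; HR 1.25, 1.5 or 2.0 per SD is assumed. Both models contain a score for the listed covariates (assumed HR 1.25 per SD), and S/F is then added. Residual correlation between endpoints is 0.5. The planned HRs are read as effects without covariates, as SAP 6 simulates them. There are 10,000 trials per setting (SE of a paired gain 0.04 to 0.37 points).

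| Power without → with S/F (%) | HR 1.25 per SD | HR 1.5 | HR 2.0 |
|---|---|---|---|
| Discharge alone, 0.05 | 97.17 → 97.66 | 96.74 → 98.48 | 96.98 → 99.70 |
| At least one (trial success) | 96.67 → 97.29 | 96.47 → 98.02 | 96.10 → 99.26 |
| Both | 92.24 → 93.02 | 91.96 → 94.92 | 92.09 → 97.74 |

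**Where the gain comes from.** At S/F HR 1.5 the mean discharge HR moves from 1.455 to 1.502 while its SE goes from 0.0985 to 0.0988. Then ln(1.455)/0.0985 = 3.81 and ln(1.502)/0.0988 = 4.12, so power is Φ(1.85) = 96.8% against Φ(2.16) = 98.5%, in agreement with the table. The gain is less attenuation, not a smaller SE.

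**Less favourable cases.**

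- Listed covariates explain half of S/F: gains of 0.1 / 0.5 / 0.4 points (discharge), 0.1 / 0.4 / 0.8 (success) and 0.1 / 0.9 / 1.4 (both).
- S/F HR 1.5 with 30% measurement error, 10% missing and 25% overlap with the listed covariates: discharge 98.37 → 98.93, success 97.72 → 98.30, both 94.52 → 95.59.
- Lowest gain in any setting: −0.02 points (SE 0.07).

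**Other reading.** If 1.45 is conditional on S/F, and S/F is independent of the listed covariates, discharge power goes 95.89 → 96.74, 94.45 → 96.71 and 86.82 → 96.32%.

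**Check by a simpler simulation** (one severity covariate, no listed-covariate score, 2,000 trials per setting). At HR 1.5 per SD, power for both endpoints goes 92.8 → 95.6% when the planned HRs are read as unadjusted, and 88.9 → 92.4% when read as adjusted. With smaller true effects (assumed 1.30 and 1.45), at least one endpoint gains about 1 to 15 points across HR 1.2 to 2.0 per SD.

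**Type I error.** Null, 10,000 trials, S/F HR 1.5: family-wise error is 4.6% without and 4.9% with S/F.

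**Chance imbalance.** The SE of the difference in mean S/F is √(2/305) = 0.081 SD. A gap of 0.16 SD or more has probability 0.048 (0.16/0.081 = 1.98). At exactly 0.16 SD, exp(0.16 × ln HR) = 1.036 / 1.067 / 1.117; the simulated slopes give 1.035 / 1.067 / 1.096. If half of S/F is explained, the shift is 2 / 3 / 5%.

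**Key secondary models.** In a smaller simulation with an assumed placebo rate of 10 to 20% and OR 0.55, the risk difference is unchanged and the logistic test gains 0.4 to 2.6 points.

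**The case against.** The covariate set was a deliberate choice: SAP 15 says it was limited to the variables thought to predict progression and recovery best, and the documents hold no prognostic data to set against that. The benefit rests on an assumed strength. Under the least favourable assumptions trial success gains 0.1 to 0.8 points, and the 9.5-point figure needs HR 2.0 per SD, independence from the listed covariates and the conditional reading of 1.45. Part of the gain is a change of target, since the adjusted HR is not the quantity used for sizing.

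S/F is also a coarse measure. FiO2 is read "using Table 4 below for all devices except the Venturi masks", and "Any oxygen flow records which are expressed as decimals should be rounded up to the nearest integer". The conversion tables span 0.24 to 0.81 (0.81/0.28 = 2.9-fold without Venturi masks, 0.81/0.24 = 3.4-fold with them), but that is the range of a lookup table, not evidence of how enrolled patients vary. Imbalance would be visible in the baseline summary, and its chance occurrence is already covered by the test's error rate. Key secondary events may be few (Protocol 8.5.2).

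Most of this stands as a limit on size. None of it shows a loss. SAP 15 gives no reason for omitting oxygen need. The models already condition on five covariates, so a conditional HR is nothing new. Seeing an imbalance in a table or in subgroup thirds does not adjust the primary test for it.

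**Conclusion.** The point holds as a worthwhile improvement. The planned analysis is valid, and its stated power is met at HRs of 1.45 and 1.7. The documentary facts are firm: there is no severity covariate, and a suitable one is already derived and permitted by the protocol.

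The size is modest and assumption-dependent. At a middling S/F effect (HR 1.5 per SD), with S/F independent of the listed covariates and measured without error, the gain is about 1.6 points on trial success and 3.0 on both endpoints. With error, missing values and overlap combined it is 0.6 and 1.1. Gains are larger if S/F is strong, if the planned HRs are conditional on S/F, or if the true effects are smaller than planned. No computed setting shows a loss of power beyond simulation error. Confidence is medium, because the prognostic strength of S/F is unknown.

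**What to change.** Before unblinding, add baseline S/F ratio as a continuous covariate to the SAP 7.2 list for the primary Cox and key secondary logistic models. With it:

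- pre-specify a rule for missing baseline S/F that ignores treatment arm, for example the pooled baseline mean;
- state that the HR is then also conditional on S/F;
- state that S/F enters the imputation models that reuse the primary covariates (SAP 9.1.1.3 and 9.2.1.3);
- keep the present covariate set as a sensitivity analysis.

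The cost is one line in the list, a missing-value rule, a sentence on what the HR conditions on, and one more term in the imputations. For the key secondary models, where events may be sparse, SAP 9.2.1.2 already provides the Firth method if quasi-complete separation occurs. If unblinding has already taken place, the primary model should stay as it is and the S/F-adjusted result should be labelled post hoc.

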8.1 Sample Size Determination

Success will be determined if at least one of the primary endpoints is declared statistically significant by the primary analysis. A sample size of 610 patients in total using a 1:1 randomisation ratio (305 patients per treatment arm) has been chosen to provide at least 90% power to detect a hazard ratio of 1.45 in time to hospital discharge and a hazard ratio of 1.7 in time to recovery and at least 95% power to declare statistical significance on at least one of the primary endpoints. This sample size has been calculated using a global 2-sided alpha level of 0.05 and adjusting for the Hochberg procedure to allow for multiple comparisons. This also allows for an interim analysis to assess futility after the first 300 randomised patients have completed the Day 35 visit or have withdrawn from the study.

The sample size calculation assumes a hospital discharge rate in the placebo treatment arm of 70% at Day 28, a recovery rate in the placebo treatment arm of 30% at Day 28 and a dropout rate of 25% over the 28-day evaluation period with time to dropout exponentially distributed.

By their definition the two primary endpoints are naturally correlated. This correlation has been estimated from prior study data and has also been considered in the sample size calculation.

More details regarding the sample size calculation used for the study will be provided in the SAP.

The key secondary endpoint of progression to severe disease or death within the 35-day study period will be formally tested, provided statistical significance is declared in both of the primary endpoints.

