## 6 Sample Size

A sample size of 610 subjects in total using a 1:1 randomisation ratio (305 subjects per treatment arm) has been chosen to provide at least 90% power to detect a hazard ratio of 1.45 in time to hospital discharge and a hazard ratio of 1.7 in time to recovery and at least 95% power to declare statistical significance on at least one of the primary endpoints. This sample size has been calculated using a global 2-sided alpha level of 0.05 and adjusting for the Hochberg procedure to allow for multiple comparisons. This sample size also allows for an interim analysis to assess futility after the first 300 randomised subjects (150 subjects per treatment arm) have completed the Day 35 assessment or have withdrawn from the study. The futility analysis is planned to be non-binding.

The power of the study was confirmed via simulation as follows:

Time to recovery and time to discharge in the placebo subjects were drawn from exponential distributions with rate parameters:

$$\text{Placebo Time to Sustained Recovery} \sim \text{Exp}\left(\frac{\log\left(\frac{100}{70}\right)}{28}\right) \text{ and}$$

$$\text{Placebo Time to Sustained Discharge} \sim \text{Exp}\left(\frac{\log\left(\frac{100}{30}\right)}{28}\right)$$

In the simulations, this gives the placebo arm:

- a median time to recovery (50% recovery) of approximately 54.4 days and a 30% recovery at exactly 28 days

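### SAP 7.2 names COVID-19 therapy and SNG001 batch as factors chosen to show homogeneity, but separate subgroup fits never estimate the difference between subgroup effects

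*SAP*

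**What the plan says.** SAP 7.2 has two lists of subgroup factors. The first (age, comorbidity, smoking, sex, BMI, race, symptom duration, region, breathlessness, vaccination, S/F ratio) is introduced as probable risk factors. The second holds COVID-19 related therapy at randomisation and SNG001 manufacturing batch, described as "factors of interest which have been selected so show homogeneity of the treatment effect".

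On method, SAP 7.2 says: "For subgroup analyses the subgroup variable will not be included in the models". It adds that the study was not powered for subgroups, that all such analyses are exploratory, and that a subgroup needs at least 20 patients. SAP 9.1.1.3 and 9.1.2.3 apply the primary Cox method of 9.1.1.2 to each subgroup for discharge and recovery. That method yields a hazard ratio, its 95% CI and a p-value.

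Neither document mentions a treatment-by-subgroup term. The only interactions named are treatment by visit and baseline by visit, in the BCSS mixed model (SAP 9.3.2.4). Protocol 8.9 leaves the subgroup methods to the SAP.

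**The concern.** Homogeneity is a statement about a contrast: the effect in one subgroup relative to the effect in another. A set of separate hazard ratios, each tested against 1, contains no estimate of that contrast and no statement of its uncertainty. The planned output therefore does not address the purpose that SAP 7.2 gives for the therapy and batch factors. The contrast is equally absent for every other factor.

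What is at stake is the reading of the results. With a p-value attached to every subgroup, it is easy to take significant here and not significant there as evidence that the effect differs. That pattern is common when the effect is identical, because each subgroup holds only part of the information. SAP 7.2 lists 46 subgroup levels (39 in the first list, 5 therapy categories, 2 batches), so such patterns would be expected somewhere.

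**Working it through.** **Inputs**
- Size: "A sample size of 610 subjects in total using a 1:1 randomisation ratio (305 subjects per treatment arm") (SAP 6).
- Alpha: "global 2-sided alpha level of 0.05 and adjusting for the Hochberg procedure" (SAP 6).
- Effects: "a hazard ratio of 1.45 in time to hospital discharge and a hazard ratio of 1.7 in time to recovery" (Protocol 8.1).
- Placebo rates: "assumes a hospital discharge rate in the placebo treatment arm of 70% at Day 28, a recovery rate in the placebo treatment arm of 30" per cent (Protocol 8.1).
- Dropout: "a dropout rate of 25% over the 28-day evaluation period with time to dropout exponentially distributed" (Protocol 8.1).
- Assumptions of this check: the subgroup shares, and an unadjusted two-sided 0.05 for each subgroup p-value. The documents give neither.

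The simulation text in SAP 6 gives different hazard ratios (1.35 for recovery, 1.7 for discharge). That is a separate matter; the values above are used here.

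**Step 1: reproduce the planned power.** With event rate λ and dropout rate μ, expected events per arm are 305 × λ/(λ+μ) × (1 − exp(−28(λ+μ))). For discharge, 28λ = ln(100/30) = 1.204 on placebo and 1.45 × 1.204 = 1.746 on SNG001, and 28μ = ln(100/75) = 0.288. This gives about 191 + 228 = 418 events. For recovery, 28λ = ln(100/70) = 0.357 and 1.7 × 0.357 = 0.606, giving about 80 + 122 = 202 events.

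The expected Z is ln(HR) × √events / 2:
- Discharge: 0.3716 × √418.4 / 2 = 3.80. Power at 0.05 is Φ(3.80 − 1.96) = 96.7%; at 0.025 it is 94.1%.
- Recovery: 0.5306 × √202.4 / 2 = 3.77. Power is 96.5% and 93.7%.

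The plan's claim "to provide at least 90% power to detect" these effects is reproduced.

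**Step 2: disagreement of separate p-values under one common effect.** A subgroup with share s of the events has expected Z of √s times the full value, so its power is Φ(√s × Z − 1.96). For two subgroups with powers p1 and p2, P(disagree) = p1(1 − p2) + p2(1 − p1).

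- Discharge, 50/50: 3.80/√2 − 1.96 = 0.727, power 76.6% each; 2 × 0.766 × 0.234 = 36%.
- Discharge, 80/20: powers 92.5% and 39.7%; 0.925 × 0.603 + 0.397 × 0.075 = 59%.
- Starting from a rounded 96% full-sample power, 50/50: (1.751 + 1.960)/√2 − 1.960 = 0.664, power 74.7%; 2 × 0.747 × 0.253 = 38%. At 90% and 80% full-sample power the figures are 47% and 50%.

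| Assumed split | Discharge | Recovery |
|---|---|---|
| 50/50 | 36% | 36% |
| 70/30 | 46% | 47% |
| 80/20 | 59% | 59% |
| 90/10 | 75% | 75% |
| three equal groups | 72% | 73% |

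Simulating 3,000 trials per scenario with separate Cox fits gave 35% to 39% (50/50), 47% to 48% (70/30) and 58% to 60% (80/20). With a smaller common discharge hazard ratio of 1.2 or 1.3, the calculated range over the 50/50 and 80/20 splits is 38% to 59%. A subgroup at the 20-patient minimum has about 418.4 × 20/610 = 14 discharge events and about 10% power.

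**Step 3: what an interaction contrast would give.** In the same simulated trials an interaction test at 0.05 falsely signalled heterogeneity in 4.8% to 5.5%. Its precision follows from SE = √(4/d1 + 4/d2), where d1 and d2 are the events in the two subgroups.

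- Discharge, 50/50: SE = √(8/209.2) = 0.196. The 95% CI of the ratio of hazard ratios is the estimate times or divided by exp(1.96 × 0.196) = 1.47. The ratio detectable with 80% power is exp(2.80 × 0.196) = 1.73. If one half has the planned effect and the other none, power is Φ(0.3716/0.1956 − 1.96) = 48%.
- Recovery, 50/50: the corresponding figures are 1.74, 2.20 and 47%.
- At 80/20 the CI factor is 1.61 for discharge and 1.99 for recovery.

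**The case against.** The best defence is that the analyses are already labelled unpowered and exploratory, and that each subgroup gets a hazard ratio and 95% CI as well as a p-value, so estimates can be compared by eye. The SAP sets no rule that judges consistency by significance, so the disagreement rates describe a habit of readers and not a decision rule in the plan. This stands, and it keeps the point minor. It does not supply the missing contrast.

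An interaction test is also weak, and a non-significant one shows homogeneity no better than separate p-values do. That stands too, which is why the ratio of hazard ratios with its CI should be the main output.

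Three stronger readings are tempting, and the documents do not support them:
- *That every subgroup analysis aims to show homogeneity.* SAP 7.2 states that aim only for therapy and batch; the other factors are listed as probable risk factors.
- *That continuous age and symptom duration are dropped from the age and duration subgroup models.* The sentence can be read that way, but the subgroup variable may equally mean the category, which is never a covariate. For sex, region and vaccine status, leaving the covariate out costs nothing because it is constant within the subgroup. The wording is ambiguous, and no more can be said.
- *That one interaction model fits every listed factor.* Batch describes the active product and the SAP assigns no batch to placebo patients. The therapy categories overlap and have no stated not-receiving group. Age, symptom duration and breathlessness each have more than one cut scheme.

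**Conclusion.** The point holds as a low-severity gap between aim and method. For therapy and batch, the plan states an aim that its analyses cannot meet; for all other factors, the difference between subgroup effects is simply not estimated. Under an identical true effect at the planned size, separate p-values would disagree in roughly 36% to 38% of trials for two equal subgroups and about 59% for an 80/20 split. These figures rest on assumed shares, 0.05 per subgroup and full-sample power of about 96% to 97%. The primary analysis, its alpha and the sample size are not affected.

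**What to change.** In SAP 7.2, with cross-references from 9.1.1.3 and 9.1.2.3:
- For each factor and each cut scheme that forms mutually exclusive groups, fit one Cox model in the full ITT set with the factor and its interaction with treatment. For therapies, use a receiving versus not-receiving contrast for each therapy.
- Report the subgroup hazard ratios, the ratio of hazard ratios with its 95% CI, and the interaction p-value, labelled exploratory.
- State that continuous age and symptom duration stay in the model for the age and duration subgroups.
- Leave batch out of the interaction models unless a placebo comparator for each batch is defined.
- State that a non-significant interaction is not evidence of homogeneity.

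The cost is SAP wording, some programming and extra columns in the subgroup outputs. None of the forest plots specified in SAP 9.1.1.2, 9.2.1.2 and 9.3.2.1 sets subgroup levels side by side, so this is not just a column added to an existing figure. No new data are needed. The downside is the low interaction power shown above.
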